### **Study Design:**

Approximately 450 baseline tau PET scans and up to 450 longitudinal scans with the  $^{18}\text{F}$ -AV-1451 ligand will be conducted on 450 subjects who are currently enrolled in one of two funded studies:

- A DOD funded grant entitled: *Effects of traumatic brain injury and post-traumatic stress disorder on Alzheimer's disease in Vietnam Veterans using ADNI (DOD ADNI) / with and without MCI.*
- A National Institute on Aging (NIA) funded grant entitled: *The Alzheimer's Disease Neuroimaging Initiative (ADNI2)*

The 450 subjects will be divided into 9 groups of approximately 50 subjects each for a baseline scan and up to 450 subjects will be re-scanned after approximately 12 months. The nine groups are listed below:

- Six groups of Vietnam Veterans will be drawn from subjects enrolled in the DOD ADNI study.
  - Three groups of Vietnam Veterans **who meet criteria for normal cognition** with history of:
    - PTSD only
    - TBI only and/or both TBI and PTSD
    - Controls (no history of TBI and/or PTSD)
  - Three groups of Vietnam Veterans who **meet criteria for mild cognitive impairment (MCI)** with a history of:
    - PTSD only
    - TBI only and/or both TBI and PTSD,
    - Controls (no history of TBI and/or PTSD)

- Three groups of civilian subjects (who are not Vietnam Veterans) and who have no history of TBI and/or PTSD will be drawn from subjects enrolled in ADNI2. These subjects will meet criteria for one of the three groups listed below:
  - Normal cognition,
  - MCI
  - Dementia due to AD

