### **Sample Size:**

Utilizing the same subject groups in each of the main DOD and NIH ADNI studies, for those subjects that consent to the Tau scan, the goal is to conduct 50 baseline  $^{18}\text{F}$ -AV-1451 ligand scans in each group and up to 50 longitudinal scans within each group (see below). Subjects will receive their initial (baseline)  $^{18}\text{F}$ -AV-1451 PET scan at their next scheduled visit. Longitudinal scans will occur approximately 12 months after their initial scan.

All DOD ADNI Vietnam Veteran subjects enrolled in the baseline procedures will be asked to complete a baseline Tau scan as well as a longitudinal scan.

ADNI2 subjects will be selected for the  $^{18}\text{F}$ -AV-1451 scan based on the following:

- **Site location:** Subjects will be eligible to participate in the addendum if their enrolling site is in a location in which the  $^{18}\text{F}$ -AV-1451 ligand is available.
- **Date of ADNI visit:** Subjects will be eligible for participation in the addendum as they come in for their scheduled ADNI-2 visit.
- **Clinical status:** Controls, Subjects with MCI, or Subjects who converted to a diagnosis of AD during ADNI-2 will be eligible; and
- **Florbetapir SUVR:** Subjects with and without evidence of amyloid deposition will be identified based on review of Florbetapir SUVR and will be invited to participate.

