#### **Addendum Design and Schedule:**

- Approximately 450 participants will participate in the  $^{18}\text{F}$ -AV-1451 PET addendum.
- ECG with results reviewed prior to  $^{18}\text{F}$ -AV-1451 dose administration.
- Approximately 450 subjects (50 from each cohort) who have consented to the Addendum will complete a Tau PET scan with  $^{18}\text{F}$ -AV-1451 PET scan at their next scheduled visit for DOD-ADNI and/or ADNI-2. For newly enrolled subjects enrolling in the DOD-ADNI study, the Tau PET scan will be performed at the baseline visit. Flortbetapir scans and the  $^{18}\text{F}$ -AV-1451 scans must be at least 16 hours apart; there is no maximum time limit to obtain the two scans.
- Up to 450 subjects (50 from each cohort) will be asked to do a follow-up Tau PET scan. The follow-up scan will be conducted 12 months after their initial scan.
- In the case of early discontinuation from the DOD-ADNI or ADNI-2 studies, the final  $^{18}\text{F}$ -AV-1451 PET scan will be obtained at the time of the early discontinuation visit if at least 3 months have passed since the most recent  $^{18}\text{F}$ -AV-1451 scan.
- Site investigators, patients, and caregivers will not be informed of the results of the  $^{18}\text{F}$ -AV-1451 PET scan results as they relate to the study; however, any findings that may be of potential medical concern will be provided for appropriate follow-up.
- Females of childbearing potential are to have a urine pregnancy test (HCG) on the day of the  $^{18}\text{F}$ -AV-1451 PET imaging session, before  $^{18}\text{F}$ -AV-1451 dose administration.
- $^{18}\text{F}$ -AV-1451 PET scans should be performed at least 16 hours apart from the  $^{18}\text{F}$ -flortbetapir PET scans due to the half-life of fluorine 18.
- Specific imaging acquisition protocols designed to ensure consistency across sites will be provided in an operations manual.

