**Longitudinal hypotheses:** Change in tau, as measured by differences between the time 2 and time 1 images will be the primary outcome when assessing associations with A $\beta$  deposition or history of TBI. A $\beta$  deposition (florbetapir SUVR) will first be considered as a continuous variable, though secondary analyses will compare change in tau in those that are A $\beta$  positive versus A $\beta$  negative. Linear regression, similar to that described above for Hypothesis 2, will be used to assess associations or differences between groups while adjusting for potential confounders of age and Apoe4 status. Finally, to assess associations between change in tau and change in episodic memory, the primary analytic strategy will use an extension of the repeated-measures, random effects models called simultaneous modeling, which utilizes the repeated-measures of both tau and episodic memory simultaneously in the same model. This technique allows for different observation times for the different outcomes, different predictors for each outcome (such as age, education, or Apoe4 status), and estimates of the between- and within-person variability. Model validation will be carried out using analytic and graphical techniques to check the core assumptions about linearity, homoscedasticity, multivariate normality, and independence of the within-person residuals beyond the person specific random effects. Hypotheses will be supported if there is a significant correlation between change in tau and change in episodic memory. Alternative strategies, if the simultaneous models do not converge, include linear regression models that use change in episodic memory as an outcome and change in tau as a predictor.

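### The longitudinal Aβ and TBI regressions use an unscaled tau difference, although the interval between scans can run from 3 to about 12 months

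*Protocol*

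**What the plan says.** The protocol places the second scan at one nominal time. Study Design says "up to 450 subjects will be re-scanned after approximately 12 months", Sample Size says "Longitudinal scans will occur approximately 12 months after their initial scan", and Addendum Design and Schedule says "The follow-up scan will be conducted 12 months after their initial scan".

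The same schedule section adds a second route to a last scan. For a participant who leaves the parent study early, the final tau scan "will be obtained at the time of the early discontinuation visit if at least 3 months have passed since the most recent" tau scan.

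Under Analyses for Addendum Hypotheses, the longitudinal paragraph sets the outcome for the Aβ and TBI associations: "Change in tau, as measured by differences between the time 2 and time 1 images will be the primary outcome". The method is linear regression of the Hypothesis 2 kind, "while adjusting for potential confounders of age and Apoe4 status". The paragraph contains no annualisation, no covariate for time between scans, no visit window and no rule on early scans.

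The association between tau change and memory change is handled differently, by a simultaneous random-effects model. Of this the protocol says "This technique allows for different observation times for the different outcomes". If that model does not converge, the stated alternative is a regression of one change score on the other, again with no interval term.

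**The concern.** A difference between two images measures change over whatever time separated them. If some second images come at 3 months and others at 12, the outcome mixes quantities that differ up to fourfold in follow-up time, and the regression has nothing to tell them apart.

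Two consequences follow. First, short intervals dilute the association between Aβ and tau change and add variance unrelated to Aβ. Second, if participants with a TBI history leave early more or less often than others, their mean change differs for reasons of timing alone. The second effect is a bias, and a larger sample does not remove it. Both bear on named primary longitudinal tests. The exploratory section also frames its hypothesis in terms of a rate of tau progression, which an unscaled difference over unequal intervals does not measure.

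**Working it through.** **Inputs from the protocol.** Planned interval 12 months (1 year); minimum interval for an early-discontinuation scan 3 months (0.25 year); longitudinal N = 180; detectable correlation 0.21 at α = 0.05 and 0.25 at α = 0.01, 80% power; detectable TBI difference 0.91 SD. The early-discontinuation rate is not given, so every rate below is an assumption.

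**The plan's own figure.** With Fisher's z and a two-sided test, r = tanh[(z for α + z for power)/√(N − 3)].
- α = 0.05: tanh[(1.960 + 0.842)/√177] = 0.208, against the stated 0.21.
- α = 0.01: tanh[(2.576 + 0.842)/√177] = 0.251, against the stated 0.25.

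Both reproduce. Power at r = 0.21 is 81.0%. These figures make no allowance for unequal intervals.

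**Aβ slope.** Let observed change = annual rate × T + scan error, with T in years. Suppose a share q has T = 0.25, the rest T = 1, and T is unrelated to Aβ. The slope is then multiplied by the mean of T: (1 − q) + 0.25q = 1 − 0.75q.
- q = 5%: 0.9625
- q = 10%: 0.925
- q = 20%: 0.85
- q = 30%: 0.775

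**Power for the Aβ association at N = 180.** This was simulated with one million subjects per setting. Assumptions: true correlation 0.21 at 12 months, linear change, half the variance of 12-month change from true rates and half from scan error, and mean annual change of 0 to 2 SD of the 12-month change.

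| Share scanned early | All at 3 months | Spread evenly over 3–12 months |
|---|---|---|
| 5% | 75–79% | 78–81% |
| 10% | 68–77% | 76–79% |
| 20% | 56–71% | 71–78% |
| 30% | 47–66% | 67–75% |

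With no early scans the simulation gave 80–82%, so differences of a point or so are simulation noise.

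**TBI contrast with equal true rates.** If shares q₁ and q₀ of the two groups are scanned at T years and the rest at 1 year, the false difference is (1 − T)(q₁ − q₀) × mean annual change.
- 20% of TBI and 5% of non-TBI participants scanned at 6 months: observed means are 0.8 + 0.2 × 0.5 = 0.900 and 0.95 + 0.05 × 0.5 = 0.975 of the annual change. The difference is 0.075 (ratio 0.923).
- 30% versus 10% at 6 months: 0.85 versus 0.95, a difference of 0.10 (ratio 0.895).
- 20% versus 10% at 3 months: 0.75 × 0.10 = 0.075.

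**On the plan's scale.** If mean annual change equals 1 SD of change, the first example is a false difference of 0.075 SD; at 2 SD it is 0.15 SD. The stated detectable difference is 0.91 SD. Mean annual change would have to be about 0.91/0.075 ≈ 12 SD for the first example to reach it.

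**The case against.** **The protocol never calls the discontinuation scan the time-2 image.** This is correct. A reader might infer that the plan states that 3-month and 12-month changes are pooled, and it does not. But that scan is described as the final one, the design has two scans, and no rule excludes it. Pooling is the natural reading, though an inferred one.

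**Windows and annualisation belong in an analysis plan, which is not shown.** An analysis plan could add them without contradicting the protocol. Even so, the protocol names the outcome, the model and covariates, and a plan that simply followed it would carry the problem forward. This is therefore more than an omitted detail.

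**The protocol does allow for timing.** A reader might infer that no longitudinal analysis does so. The primary tau–memory model accommodates different observation times and is not at issue. The gap is confined to the Aβ and TBI regressions and the change-score fallback. Nor should the covariates be read as strictly age and Apoe4: the regression is modelled on Hypothesis 2, which also carries education. Scan interval appears in neither list.

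**The bias is usually toward the null.** A reader might infer this, but it does not hold in general. Dilution of the Aβ slope is toward the null when early scanning is unrelated to Aβ. The TBI example starts from equal true rates and produces a false deficit, which is away from the null. Differential discontinuation by TBI history or cognition is plausible but undocumented.

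**The effect may be small.** This stands. With few early scans, or scans mostly well after 3 months, the loss is modest, and the TBI examples are small against 0.91 SD.

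**Conclusion.** The point holds for the Aβ and TBI regressions and for the tau–memory fallback. Followed as written, the protocol lets changes over 3 to about 12 months enter one outcome as if they were equivalent.

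The size cannot be fixed from the document. It rests on linear change and on an assumed share and timing of early scans: a 7.5% to 15% loss of Aβ slope for 10% to 20% scanned at 3 months, and little at 5% or less. Any TBI bias needs discontinuation to differ between groups and is proportional to mean annual change, so it vanishes if that mean is near zero. The direction depends on the true effect and on who discontinues. It is worth correcting before analysis because the outcome is a named primary one and the remedy is inexpensive.

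**What to change.** In the longitudinal paragraph of Analyses for Addendum Hypotheses:

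- Replace the unscaled difference for the Aβ and TBI tests with a longitudinal model of tau on actual years since the baseline scan. Take time-by-Aβ and time-by-TBI as the tests, and keep all baseline scans.
- Include a random slope where it can be estimated, and otherwise use robust standard errors. A random intercept alone can misstate standard errors when individual rates vary and intervals are unequal. With at most two scans per person, a random slope may prove hard to estimate, so the alternative should be named in advance.
- Apply the same handling of the interval to the change-score fallback for tau and memory.
- Avoid unweighted division by the interval: dividing by 0.25 year gives a 3-month scan 1/0.25 = 4 times the error SD of a 12-month scan.
- State whether an early-discontinuation scan counts as the second image, and report participants rescanned at about 12 months as a sensitivity analysis.

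The cost is slightly more analysis work. It needs actual scan dates, which the protocol does not expressly say are recorded, although its 3-month and 12-month rules cannot be applied without them. The scan schedule does not change.

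### With at most two tau scans per person, the primary joint model cannot reliably separate tau change from scan error, so the size of its tau-memory change correlation is undetermined or very imprecise

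*Protocol*

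**What the plan says.** The protocol section Analyses for Addendum Hypotheses (Longitudinal hypotheses) adopts simultaneous modelling as the primary strategy for tau change against episodic-memory change. The model "utilizes the repeated-measures of both tau and episodic memory simultaneously in the same model" and is credited with "estimates of the between- and within-person variability". Its assumptions include "independence of the within-person residuals beyond the person specific random effects". The criterion is "Hypotheses will be supported if there is a significant correlation between change in tau and change in episodic memory". Regression of memory change on tau change is listed under "Alternative strategies, if the simultaneous models do not converge".

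On tau data, the same paragraph says "Change in tau, as measured by differences between the time 2 and time 1 images will be the primary outcome", which is two occasions. Study Design says "up to 450 subjects will be re-scanned after approximately 12 months", while Addendum Design and Schedule says "The follow-up scan will be conducted 12 months after their initial scan". The latter section also allows a final scan at early discontinuation once 3 months have passed since the last one. The number of memory assessments is not given in this addendum.

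Power considerations gives a detectable correlation of 0.21 (alpha 0.05) or 0.25 (alpha 0.01) with 180 people.

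**The concern.** A correlation between two person-specific rates of change divides their covariance by the two slope standard deviations. For tau, the slope variance has to be told apart from scan-to-scan error. Two scans per person at the same spacing carry no information on that split, because a large observed change may be true change or noise.

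At stake is the quantity that the protocol names as its criterion. If the tau slope variance is undetermined, so is the latent correlation, and a Wald test or confidence interval built on it has no sound basis. The claimed separation of between- and within-person variability for tau fails for the same reason. The safeguard is tied to non-convergence, but an optimiser can stop at an arbitrary point on a flat likelihood and report convergence.

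**Working it through.** **1. The plan's own figure.** By Fisher's z, n = ((z_alpha/2 + z_power)/atanh(r))^2 + 3.
- r = 0.21, alpha 0.05: ((1.960 + 0.842)/0.2132)^2 + 3 = 175.7. Power at n=180 is 0.81.
- r = 0.25, alpha 0.01: ((2.576 + 0.842)/0.2554)^2 + 3 = 182.0. Power at n=180 is 0.795.

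Both reproduce. This is the power of an ordinary correlation between 180 pairs of values, not of a latent slope correlation.

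**2. Tau moments at common spacing.** Let a be the tau intercept variance, c the intercept-slope covariance, b the slope variance and e the scan-error variance. With scans at 0 and 1 year and independent residuals:
- Var(scan 1) = a + e
- Cov(scan 1, scan 2) = a + c
- Var(scan 2) = a + 2c + b + e

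There are three equations for four unknowns. Adding d to a, -d to c, +2d to b and -d to e leaves all three unchanged. The observed change fixes only b + 2e. The Fisher information for the four parameters has rank 3. In the joint model with three or more memory occasions (12 parameters, tau and memory residuals independent), the rank is 11. With memory also seen only at 0 and 12 months, it is 10.

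**3. Effect on the correlation (assumed values).** Take memory slope variance 0.09 and slope covariance -0.004.
- Set A: b = 0.0009, e = 0.0009, so b + 2e = 0.0027. Correlation = -0.004/sqrt(0.0009 x 0.09) = -0.44.
- Set B (d = 0.0006): b = 0.0021, e = 0.0003, so b + 2e = 0.0027. Correlation = -0.004/sqrt(0.0021 x 0.09) = -0.29.

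The two sets imply the same covariance matrix for the data, so no sample of this design can choose between them.

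**4. What stays identified.** Let h be the tau-slope/memory-slope covariance and k the tau-slope/memory-intercept covariance. The covariance of observed tau change with memory at time s is k + s x h. Tau scan error does not enter, so two or more memory occasions identify h. It is -0.004 in both sets, and a likelihood-ratio test of h = 0 is unaffected by the flat direction.

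**5. Does timing spread rescue the split?** The information is I_jk = sum over persons of 0.5 x tr(V^-1 dV_j V^-1 dV_k), where V is the covariance of a person's two scans. The documents give neither the spread nor the variances, so both are assumed. Reliability of tau change means b/(b + 2e): 1/3 for b = e, 2/3 for b = 4e. Entries are SE(b)/b.

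| Scan timing | n=450, rel. 1/3 | n=450, rel. 2/3 | n=180, rel. 1/3 | n=180, rel. 2/3 |
|---|---|---|---|---|
| All at 12 months | not identified | not identified | not identified | not identified |
| SD 1 month | 1.21 | 0.60 | 1.91 | 0.95 |
| SD 2 months | 0.62 | 0.30 | 0.98 | 0.48 |
| SD 1 month, 10% at 3-9 months | 0.61 | 0.23 | 0.96 | 0.36 |

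These use the expected spread of timing; one random draw of 180 scan dates with a 1-month SD gave 2.07 and 1.03. In the last row, much of the information comes from early discontinuers and assumes that their slope variance equals that of completers.

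**The case against.** The strongest reply is that the protocol never writes out the random effects or names a random tau slope, and that such detail is often left to the analysis plan. That is true, and the point is conditional on it. But a tau part with only a random intercept has no person-level change to correlate, so the stated criterion implies a slope or an equivalent term.

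A reader might infer that the model cannot be estimated at all. The documents do not support that: intervals of approximately 12 months, and early scans from 3 months, make the variances formally identifiable. Under favourable assumptions at n=450, the relative standard error falls to 0.23-0.30.

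A reader might also infer that the decision on the hypothesis depends on software starting values. That too goes too far. The criterion is significance, and a likelihood-ratio test of zero covariance gives the same answer anywhere on the flat ridge. What is lost is the size of the correlation and any Wald inference on it.

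Finally, a usable regression is already listed and model validation is planned. Both count in the plan's favour, but the listed checks cover linearity, variance, normality and independence rather than identifiability, and the switch is tied to non-convergence alone.

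**Conclusion.** The point holds in a limited form. If tau change enters as a random slope, its variance cannot be separated from scan error at common 12-month spacing. With a 1-month SD of timing it is poorly estimated: the standard error is about 60-120% of the value at n=450 and 95-190% at n=180. With wider spread or 10% early scans, it ranges from 23% to 98% across the cases shown. The latent correlation and the tau variance split inherit this, while the slope covariance and a likelihood-ratio test of it do not. The rank results rest on the scan schedule and independent residuals. The percentages rest on assumed variances and timing. The protocol fixes the two-scan design, the primary model, the criterion and the fallback trigger, and these do not fit together.

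**What to change.** Preferred: make the listed regression primary, without the non-convergence condition. Regress memory change (or memory slope) on observed tau change per year, adjusted for age, education and Apoe4, and report the joint model as exploratory. No data collection changes, and the power statement already describes a correlation of this kind.

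The cost is attenuation by tau scan error, which should be stated. If the latent correlation were 0.21, the observed one would be 0.21 x sqrt(reliability): 0.18, 0.15 or 0.11 at tau-change reliability 0.75, 0.50 or 0.25. Power at n=180 would then be 0.69, 0.51 or 0.29. The 0.21 should therefore be described as a correlation with observed tau change. People without a second scan also drop out of this regression.

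Alternative: keep the joint model primary with an explicit random tau change and base the criterion on the likelihood-ratio test of the tau-change/memory-slope covariance. State that the latent correlation and the tau variance split will not be interpreted, and extend the fallback trigger to a singular or near-singular information matrix.

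A random intercept alone for tau is not a way out. The intercept cancels from the difference between scans, so the model forces the covariance of interest to zero.
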